## **1. Project Summary**

JointCOACH is a web-based communication platform that enables joint replacement patients to communicate with their care team via computer or smartphone throughout their episode of care, from the time that surgery is scheduled until at least 90 days postoperatively. Patients will receive the following information at key intervals: 1) instructions about how to prepare for surgery, 2) information about the procedure, 3) information about medications and pain control, 4) information about postoperative recovery and rehabilitation. In addition, several surveys will be distributed using JointCOACH to keep patients involved in their own recovery and to keep the surgical team informed of their progress. The proposed research will help determine if JointCOACH can improve patient satisfaction and clinical outcomes.

## **2. Introduction and Background**

Health systems invest significant resources to improve quality and reduce costs. However, this process is typically driven by hospital administration and staff. Recently, studies have shown that when patients are engaged, they take more responsibility for their own health and preventative care. Additionally, these patients are more satisfied with their healthcare experiences and have lower rates of healthcare utilization . Physicians are in the best position to promote patient engagement since they have direct relationships with their own patients. However, physicians need frictionless tools with minimal implementation barriers in order to create and maintain this relationship in the follow up period.

Patient engagement has been referred to as the next blockbuster “drug”, and increasing evidence demonstrates that highly engaged patients not only enjoy improved outcomes, but have fewer complications, undergo fewer readmissions, and have lower total costs of care . While these engagement-related outcomes have been shown in several other specialties, relatively little has been done to explore this relationship in orthopedics. The opportunity to demonstrate the

impact of engagement on outcomes in the orthopedic space is highlighted by the estimated \$1.5B of medical expenses occurring nationally due to potentially preventable readmissions following orthopedic surgeries alone.

Stryker Performance Solutions JointCOACH™ and the Cleveland Clinic are interested in collaborating on a clinical pilot study to demonstrate that high patient engagement leads to enhanced preoperative preparation potentially reducing length of stay (LOS), readmissions and reoperations, increasing discharge disposition to home rather than another facility, reducing the need for in-person follow up, and increasing patient (and provider) satisfaction after elective primary hip and knee arthroplasty (THA and TKA). These improvements can translate to higher financial savings through the episode of care especially in light of the alternative payment models.

### **3. Specific Aims**

Currently in use by orthopedic groups around the country, JointCOACH improves perioperative outcomes after THA and TKA and mitigates risk by: 1) enhancing patient engagement with providers, 2) allowing patients to play an integral role in patient-reported outcomes, 3) generating and relaying actionable pre- and postoperative reporting directly to the clinical team, and 4) detecting impending postoperative complications early, enabling timely intervention and preventing avoidable complications and readmissions. The specific aims of this proposal are to:

1. Measure patient satisfaction with and without use of JointCOACH as a tool for patient engagement
2. Understand the degree to which high postoperative engagement can reduce the amount of healthcare resource utilization by answering the following questions:

- a. Will the use of JointCOACH decrease the number of potentially avoidable healthcare utilization encounters such as Emergency Department (ED) and hospital visits (i.e. readmissions and reoperations)?
  - b. Does utilizing JointCOACH improve clinical workflow by minimizing telephone calls and thereby offloading support staff, allowing them to be more efficient?
  - c. Does utilizing JointCOACH reduce the volume of on-call pages by addressing patient questions up front, alleviating concerns, and providing them with the information they need when they need it?
  - d. Does utilizing JointCOACH allow the practice to identify patients whose in-person follow-up needs are minimal?
3. Measure additional potential benefits including shorter length of hospital stay, discharge disposition to home rather than a facility and decreased 90 day readmissions and reoperations by answering the following:
  - a. Does utilizing JointCOACH lead to early detection of adverse signs/symptoms that develop between clinical encounters and result in reduced readmissions and reoperations?
4. Evaluate the financial impact of JointCOACH in the episode of care (% difference in Charges between JointCOACH and standard of care groups)

## **4. Methods**

### **4.1 Study Design**

The study design is a prospective, randomized trial in which patients undergoing elective primary hip or knee arthroplasty will be offered perioperative use of JointCOACH vs standard of care. A total of 400 patients will be enrolled (200 in each group). The following outcome measures will be collected at the intervals specified in the Schedule of Events:

- Demographics (Age, gender, BMI)
- Comorbidities (Age-Adjusted Charlson Comorbidity Index)
- Surgical details (ASA (or other comorbidity index), Length of surgery (incision to closure), procedure type, operative limb, surgeon)
- Length of hospital stay and discharge disposition
- Number of ED visits and follow-up visits within 90 days
- Number of phone calls and on-call pages within 90 days
- Readmissions and reoperations within 90 days
- Patient satisfaction (VAS satisfaction and PPE-15)
- Provider satisfaction (5-point Likert scale)

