#### 4.4 Schedule of Events

Evaluation	Preop	Intraop	Inpatient	D1	D2	D3	D4	D6	D8	D10	D12	W1-2	W4-6	D30	D90
Demographics	X														
Medical History / Comorbidities	X														
Surgical Details		X													
Discharge (LOS, disposition)			X												
Track Readmission / Reoperation													X	X	
Track ED visits, office visits													X	X	
Track calls and on-call pages													X	X	
Adverse Events	X	X											X	X	
Postop Check-in Check-up				X	X	X	X	X	X	X	X				
Recovery Goals												X	X		
HOOS Jr / KOOS Jr	X													X	
Promise 10	X													X	
Patient Satisfaction (VAS and PPE-15)														X	X
Provider Satisfaction (5-point Likert)															X

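### Aim 2b infers relief of support staff from fewer telephone calls, but no outcome counts the staff work that arrives through JointCOACH itself

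*Combined protocol and SAP*

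**What the plan says.** Section 3 (Specific Aims) puts two neighbouring questions. Aim 2b asks: "Does utilizing JointCOACH improve clinical workflow by minimizing telephone calls and thereby offloading support staff, allowing them to be more efficient". Aim 2c asks: "Does utilizing JointCOACH reduce the volume of on-call pages by addressing patient questions up front". The first moves from a call count to a statement about staff workload. The second concerns page volume alone.

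The outcome serving both is one line in Section 4.1, "Number of phone calls and on-call pages within 90 days", matched by one row in Section 4.4, "Track calls and on-call pages".

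Section 1 describes the intervention as a platform that "enables joint replacement patients to communicate with their care team via computer or smartphone throughout their episode of care" and adds that surveys sent through it keep the surgical team informed. Section 3 lists among its functions "generating and relaying actionable pre- and postoperative reporting directly to the clinical team".

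**The concern.** The intervention adds a contact channel in one arm, and the outcome counts only the older channels. A question that would have been telephoned may arrive through the platform, and a report may prompt a staff action that would not otherwise have occurred. Neither is counted unless it ends in a call or a page. A fall in calls in the JointCOACH arm could therefore mean less work, the same work by another route, or more work in total.

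Randomisation does not settle this, because the difficulty lies in what is measured and not in who is compared. At stake is the workflow conclusion of Aim 2b: a trial run exactly to plan could report fewer calls and still not know whether support staff were relieved.

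**Working it through.** **Step 1. Is there a planned figure to reproduce?** No. The documents state no expected rate of calls, pages or platform contacts. The sample size in Section 4.3 concerns the PPE-15 and has no bearing here.

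**Step 2. Is platform work counted anywhere?** The places where it might be:

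| Place | What it covers | Counts staff-handled platform contacts? |
|---|---|---|
| 4.1 Study Design, outcome list | Calls and pages; visits; satisfaction | No |
| 4.4 Schedule of Events | Tracking row for calls and pages; eight check-ins (D1, D2, D3, D4, D6, D8, D10, D12) | No; the check-ins are scheduled, but staff responses to them are not recorded |
| 4.5 Data Analysis Plan | The PPE-15 comparison only | No |
| 6.1 Study Metrics | Patient utilization and compliance; follow-up visits | No; patient use and visit counts |
| 6.3 Success Thresholds | Share of patients engaged with the software | No; patient side only |
| Provider Satisfaction Survey | Role, satisfaction, likelihood of recommending | No; no workload item and no comparison between arms |

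**Step 3. What can the planned count distinguish?** Let C be calls per patient in the control arm, f the proportional fall in calls in the JointCOACH arm, and r the number of staff-handled platform contacts that replace each avoided call. For simplicity, pages and other electronic messages are held equal between arms and left out.

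- Planned measure: [C(1 − f) − C] / C = −f
- All contacts: [C(1 − f) + C·f·r − C] / C = −f(1 − r)

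C cancels, so no assumption about the call rate is needed. The values of f and r below are assumptions; the documents supply neither.

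| Assumed r | f = 20%: planned | f = 20%: all contacts | f = 40%: planned | f = 40%: all contacts |
|---|---|---|---|---|
| 0 | −20% | −20% | −40% | −40% |
| 0.5 | −20% | −10% | −40% | −20% |
| 1.0 | −20% | 0% | −40% | 0% |
| 1.5 | −20% | +10% | −40% | +20% |

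For example, with f = 0.40 and r = 1.5: −0.40 × (1 − 1.5) = +0.20.

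**Step 4. Reading.** The planned columns do not change with r, so the planned data carry no information about r. The rows run from full relief (r = 0) through pure channel switching (r = 1) to added contacts (r above 1), and the planned outcome gives the same answer for all of them. That conclusion does not depend on which values of f and r are chosen.

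**The case against.** The strongest reply is that Aim 2b names fewer telephone calls as its mechanism, and the call count measures exactly that. This stands: counts of calls and pages are valid as such, and only the further step to staff relief and efficiency lacks support.

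A reader might infer that Aim 2c fails in the same way. It does not. It asks about page volume, and the page count answers it.

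A reader might also infer that the plan is biased, and always in favour of JointCOACH. The documents do not show this, for three reasons:

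- If information given in advance removes the need for contact, there is no replacement and no bias (r = 0 above). Aim 2c describes such a mechanism for pages.
- The plan does not say whether outgoing calls count. If they do, a check-in response that leads staff to telephone a patient would raise the JointCOACH total.
- Control patients may use other electronic messages, also uncounted, which would pull the other way.

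Nor can the uncounted work be sized from the eight check-ins. No document says how often a response leads to staff action. That the check-ins run through JointCOACH is itself inferred from Section 1. They are also solicited monitoring, not patient questions moved from the telephone.

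Finally, a total that adds contacts with equal weight treats a brief look at a report like a telephone call. It is not a measure of staff time and could count against JointCOACH. This also stands, and is why the components should stay visible.

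**Conclusion.** The point holds for the inference in Aim 2b. The planned outcome cannot separate real relief of staff from contact that has moved to the platform. If contacts do move, the count would overstate the relief or imply it wrongly. Whether they will is unknown, so this is an undetectable risk and not a demonstrated bias.

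Its size cannot be derived from the documents. Under the assumed range of 0 to 1.5 replacement contacts per avoided call, a 40% fall in calls is compatible with a change in total contacts from −40% to +20%. The conclusion rests on the protocol's own description of JointCOACH as a channel to the care team, and on the absence of any count of that traffic. Aim 2b is a secondary question, and the PPE-15 primary analysis does not depend on it.

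**What to change.** For Aim 2b, add an outcome: JointCOACH contacts handled by staff within 90 days, meaning patient messages and check-in responses that lead to a staff action. Take these from the platform log if it records staff handling; otherwise record them prospectively from the start. Report them beside calls and pages, and as a per-patient total by arm. Count other electronic messages in the same way in both arms where they are routinely available. Keep calls and pages as separate components, and leave Aim 2c as it is.

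If platform contacts cannot be counted, limit the Aim 2b conclusion to telephone call volume and drop the claim about relief and efficiency of staff. This option needs only a change of wording.

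The cost of the fuller option is more than a single export. The documents do not say that the log identifies items handled by staff, and other electronic messages lie outside the platform. The total would be unweighted and would not measure staff time, and the result may be less favourable to JointCOACH. No new sample size follows, because the documents give no contact rates.

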## 4.2 Patient Population

The Cleveland Clinic Orthopedic Institute practice patients from Main Campus surgeons ([name], [name], [name], [name], [name]), Lutheran Hospital surgeons ([name], [name]), Marymount surgeons ([name], [name]), and Medina Hospital surgeons ([name]) will be assessed for eligibility.

### Inclusion criteria

1. Undergoing primary total hip or primary total knee arthroplasty
2. Willing to sign an IRB approved informed consent form
3. Have internet access or mobile access with a valid email address at the time of enrollment
4. Above the age of 18 years

### Exclusion criteria

1. Staged arthroplasty procedure within 6 months of the index procedure

2. Abandoned email address of record (e.g. bounce of email from clinic)
3. Planned discharge to a Skilled Nursing Facility

#### **4.3 Sample Size Calculation**

We will enroll 400 patients (200 in each group). This sample size was estimated using patient reported satisfaction based on the PPE-15 questionnaire as the primary endpoint. Currently, it is not known what will be a clinically relevant difference so we conservatively estimated that a 10% difference in patient satisfaction (difference in % of respondents indicating a problem on the PPE-15 between treatment and control groups) would be relevant. Based on data published in a study by Jenkinson et al, we used a mean of 24.7% ( $\pm$  7.7) for the percent of respondents across all PPE-15 domains that identified a problem with their experience. Setting alpha equal to 0.05 and power equal to 80%, we determined that we will need 153 patients in each group. However, we will enroll 200 patients in each group to account for withdrawals and non-responders.

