#### **4.5 Data Analysis Plan**

The difference in percent of respondents indicating a problem on the PPE-15 between treatment and control groups will be calculated as [percent of standard of care respondents reporting a problem, averaged across all PPE-15 domains] – [percent of JointCOACH respondents reporting a problem, averaged across all PPE-15 domains], such that a positive difference indicates that the JointCOACH group was more satisfied than the standard of care group, while a negative value indicates the opposite. A superiority hypothesis test using the two-independent sample t-test will be used to statistically evaluate the difference in the average satisfaction between groups.

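### The 153 per arm in section 4.3 is reproduced only with 7.7 as the between-patient SD and 10% read as 2.47 points; the text supports neither, so the stated 80% power is not shown

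*Combined protocol and SAP*

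**What the plan says.** Section 4.3 makes the PPE-15 the basis of the sample size: "This sample size was estimated using patient reported satisfaction based on the PPE-15 questionnaire as the primary endpoint". The target is "a 10% difference in patient satisfaction (difference in % of respondents indicating a problem on the PPE-15 between treatment and control groups". The mean of 24.7% with ± 7.7 is taken from a published PPE-15 validation study and is described as being "for the percent of respondents across all PPE-15 domains that identified a problem with their experience". The result is: "Setting alpha equal to 0.05 and power equal to 80%, we determined that we will need 153 patients in each group". Enrolment is then raised to 200 per arm to allow for withdrawals and non-response.

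Section 4.5 forms, for each arm, a quantity such as "percent of standard of care respondents reporting a problem, averaged across all PPE-15 domains" and subtracts one arm's value from the other's. It then says: "A superiority hypothesis test using the two-independent sample t-test will be used to statistically evaluate the difference in the average satisfaction between groups".

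Neither section says what ± 7.7 measures, whether 10% is relative or absolute, whether the test is one- or two-sided, or what score each patient contributes to the t-test.

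**The concern.** A two-sample t-test needs one value per patient and the SD of that value between patients. The plan supplies neither. Its only spread, 7.7, is tied to a percent of respondents across domains, which is a property of a group. The natural reading is a spread from domain to domain. Such a spread says nothing direct about how much patients differ from one another, and that is usually considerably more.

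The target is also unclear. It is worded as a difference in percent of respondents, and section 4.5 subtracts one percent from another, so a reader may well take it as ten percentage points. The stated sample size fits a difference about a quarter as large.

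This is the only power statement for the primary endpoint. If 2.47 points is the real target, a null result could be taken as evidence of no benefit when the trial had little chance of showing one. If 10 points is the target, the trial may be larger than it needs to be.

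**Working it through.** **Inputs from section 4.3:** mean 24.7, ± 7.7, difference 10%, alpha 0.05, power 80%, 153 per arm (200 enrolled). Sidedness is not stated.

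**Step 1. Reproduce 153.** For two means, n per arm = 2(z₁₋α/₂ + z₁₋β)²(SD/Δ)².

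- Δ = 0.10 × 24.7 = 2.47, SD = 7.7, two-sided: 2 × (1.96 + 0.8416)² × (7.7/2.47)² = 152.6, so **153**. The t-based solution is 153.5, and noncentral-t power at 153 is 79.9%.
- The same inputs one-sided: 121.
- Δ = 10, SD = 7.7, two-sided: 9.3, so 10 (t-based 11).
- Two proportions, 24.7% v 14.7%, two-sided, pooled formula: 247.1, so 248.
- Two proportions, 24.7% v 22.23% (a relative 10% reduction), two-sided: 4,620.

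Only the first matches. A 10-point difference would give 153 with an SD of about 31, but no such SD appears in the documents.

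**Step 2. Could 7.7 be a patient SD?** The following are my assumptions, not the documents': the score is a patient's percent of 15 equally weighted yes/no items with a problem; the mean is 24.7%; item percents are spread by 7.7; the average inter-item correlation is ρ.

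- Mean p(1−p) = 0.247 − (0.247² + 0.077²) = 0.1801.
- Variance of the patient score = (0.1801/15)(1 + 14ρ).
- ρ = 0 gives an SD of 10.96 points. An SD of 7.7 requires 0.077² = 0.01200 × (1 + 14ρ), so ρ = −0.036.

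Under this score, 7.7 would require problem reports to be slightly negatively correlated within patients. That is implausible for items describing one hospital experience.

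**Step 3. Power, required size and detectable difference** (noncentral t, two-sided 0.05; n per arm is for 80% power):

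| ρ | SD | Power for 2.47 points, 153 (200) per arm | n per arm, 2.47 points | Power for 10 points, 153 (200) per arm | n per arm, 10 points | Detectable difference at 80%, 153 (200) per arm |
|---|---|---|---|---|---|---|
| 0 | 10.96 | 50.2% (61.4%) | 310 | >99.9% (>99.9%) | 20 | 3.52 (3.08) |
| 0.1 | 16.97 | 24.5% (30.6%) | 743 | 99.9% (>99.9%) | 47 | 5.45 (4.77) |
| 0.2 | 21.36 | 17.2% (21.1%) | 1,175 | 98.3% (99.7%) | 73 | 6.86 (6.00) |
| 0.3 | 24.98 | 13.8% (16.7%) | 1,608 | 93.7% (97.9%) | 99 | 8.03 (7.02) |

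**Step 4. Break-even SDs**, which do not depend on the item model. Power for 2.47 points is 80% only if the SD is at most 7.7 with 153 per arm, or 8.8 with 200. Power for 10 points stays at 80% or more unless the SD exceeds 31.1 with 153 per arm, or 35.6 with 200.

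**The case against.** The strongest reply is that this is a labelling gap and not a demonstrated error. The arithmetic behind 153 is correct for its inputs. The value 2.47 is never printed, so its use is inferred. The ± 7.7 comes from a publication not available here and might prove to be a patient SD. The subtraction of percents in section 4.5 favours the absolute reading, on which the trial is well powered over the SD range shown. The 14% to 50% figures rest on an assumed score and an assumed correlation range. Section 2 calls the work a clinical pilot, and section 4.3 admits that the relevant difference is unknown.

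Much of this is fair. The documents do not settle what 7.7 is, so the claim is that 80% power is not shown, not that it is absent. The ceiling of 0.3 on ρ is a choice: at ρ = 0.5 the SD is 31.0, and power at 153 per arm is 80.3% for 10 points and 10.7% for 2.47.

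The reply does not rescue the paragraph. If 10 absolute points was meant, the printed inputs do not yield 153. If 2.47 was meant, the wording does not say so. Even if 7.7 were a patient SD, the ambiguity of the 10% and the missing patient score would remain. A pilot may decline to claim power for a given difference, but this plan makes the claim.

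**Conclusion.** The point holds and should be corrected before the plan is relied on. The figure of 153 per arm matches a two-sided comparison of means with SD 7.7 and a 2.47-point difference, and no other standard calculation tried on the printed figures. The documents give no between-patient SD and no per-patient score for the section 4.5 test, so the stated 80% power has no shown basis.

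The direction of the error depends on what the sponsor meant. For a relative 10%, the reading that yields 153, the trial is underpowered for any patient SD above 7.7 at 153 per arm or 8.8 at 200; the assumed range of 11 to 25 lies wholly above both. For an absolute 10 points, that same range leaves the trial amply powered. The break-even SDs need only the t-test and two-sided 0.05; the 11 to 25 range rests on the 15-item model. Confidence is moderate, because the meaning of ± 7.7 lies in a source outside the documents.

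**What to change.** Rewrite the power paragraph in section 4.3 and add a sentence to section 4.5:

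1. Define the per-patient score, for example each patient's percent of the 15 PPE-15 items on which a problem is reported, and state that the t-test compares the mean of this score between arms.
2. State the target difference in percentage points and whether the 10% is relative (2.47 points) or absolute (10 points). State the sidedness of the test.
3. Replace 7.7 with a patient-level SD and its source. If none exists, give a range labelled as assumed, such as 11 to 25 points. If 7.7 is in fact a patient SD, say so and identify the score it belongs to.
4. Replace the 80% power sentence with a detectable difference, for example: *With 153 evaluable patients per arm and two-sided alpha 0.05, the trial has 80% power to detect a difference of 3.5 points (SD 11) to 8.0 points (SD 25).*
5. Check the assumed SD against the blinded pooled SD of early responders and report it.

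The cost is one paragraph, one sentence and a small blinded check, with no extra patients. The stated detectable difference becomes less favourable than the 2.47 points behind 153. If the sponsor confirms 2.47 points as the target, the plan must say that 400 patients do not give 80% power for it over the assumed SD range.
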